## Statistical Analysis Plan

### Brief Summary

In the present study, patients will be sent a message via patient portal after completing a medical procedure with information regarding how to call Geisinger if they have medical issues or concerns post-procedure. Researchers will assess if these patients are more likely to contact Geisinger with post-procedure medical concerns and decrease emergency department (ED) utilization.

### Project Status

Data collection is ongoing. The study team has looked at data for the purposes of identifying if messages are relevant to the patient's procedure and to ensure data are being recorded correctly. Data have been collected on 3,187 patients as of the most recent data pull.

### Power Analysis

We anticipate a ~5.8% ED utilization rate based on historic data among Women's Health patients who underwent surgical or clinical procedures. We expect to achieve about 80% power to observe a 20% reduction in visits (to 4.6% ED utilization) in either of the intervention arms relative to the control arm at a two-tailed  $p < .05$  with  $N = 5,766$  per group. This power analysis allows us the ability to detect an effect for outcomes that contrast each condition with baseline separately. Some outcomes contrast data from pooled experimental arms with the control arm. We should have power to detect an even smaller effect for outcomes that involve pooled data for experimental arms.

### Change in Time Frames

In our original preregistration, our primary outcomes and some secondary outcomes were to be measured at 12 months after the intervention began. Other secondary outcomes had 5 month timeframes. However, because recruitment has been slower than expected, we extended our outcome timeframes. Outcome timeframes that were originally 12 months have been changed to 18 months. Outcome timeframes that were originally 5 months have been changed to 12 months. At 12 months, we expect to be powered to detect at least a 25% relative decrease in ED utilization. At 18 months, we expect to be powered to detect a 20% relative decrease in ED utilization, as outlined above.

### Estimated Sample Sizes

Patients will be randomly assigned to 1 of 3 arms:

1. Control
2. Call your provider
3. Call tele-nurse

Estimated enrollment for each arm is listed below, with intervention arms highlighted in blue:

Arm	Estimated Enrollment
1. Control	5,766
2. Call your provider	5,767
3. Call tele-nurse	5,767
Total	17,300

## Planned Analyses

### Primary Outcomes

1. Phone calls [ Time Frame: N = 17,300 or 18 months, whichever occurs first ]

**Question 1:** Do patient portal messages sent after a delivery, procedure, or surgical discharge increase calls to the provider or tele-nurse?

*Analysis 1 (Confirmatory):* We will test the hypothesis that patients who are sent messages with contact information for their provider or tele-nurse are more likely to call (either phone number) within the 30 days following their procedure than those who are not sent messages. To this end, we will run an OLS regression with a binary outcome variable coding for calls (1 = call, 0 = no call) and a dummy-coded predictor variable coding for condition (1 = message, 0 = no message).

**Question 2:** Are messages that encourage calls to the tele-nurse more effective at increasing calls compared with messages that encourage calls to providers?

*Analysis 2 (Exploratory):* We will test whether tele-nurse messages or provider messages are more effective at promoting calls within the 30 days following a procedure by running an OLS regression with a binary outcome variable coding for calls (1 = call, 0 = no call) and a dummy-coded predictor variable coding for condition (1 = tele-nurse, 0 = provider).

**Question 3:** Do messages that encourage calls to the tele-nurse increase calls compared to sending no messages?

*Analysis 3 (Confirmatory):* We will test the hypothesis that patients who are sent messages encouraging them to call the tele-nurse line are more likely to call within the 30 days following their procedure than those who are not sent messages. We will run an OLS regression with a binary outcome variable coding for calls (1 = call, 0 = no call) and a dummy-coded predictor variable coding for condition (1 = tele-nurse message, 0 = no message).

**Question 4:** Do messages that encourage patients to call their provider increase calls compared to sending no messages?

*Analysis 4 (Confirmatory):* We will test the hypothesis that patients who are sent messages encouraging them to call their provider are more likely to call within the 30 days following their procedure than those who are not sent messages. We will run an OLS regression with a binary outcome variable coding for calls (1 = call, 0 = no call) and a dummy-coded predictor variable coding for condition (1 = provider message, 0 = no message).

2. ED utilization [ Time Frame: N = 17,300 or 18 months, whichever occurs first ]

**Question 1:** Do messages sent after a delivery, procedure, or surgical discharge result in fewer ED visits?

*Analysis 1 (Confirmatory):* We will test the hypothesis that patients who are sent messages encouraging them to call their provider or tele-nurse are less likely to visit the ED within the 30 days following their procedure than those who are not sent messages. To this end, we will run an OLS regression with a binary outcome variable coding for ED visits (1 = visit, 0 = no visit) and a dummy-coded predictor variable coding for condition (1 = message, 0 = no message).

**Question 2:** Are messages that encourage calls to the tele-nurse more effective at decreasing ED visits compared to messages that encourage calls to providers?

*Analysis 2 (Exploratory):* We will test whether tele-nurse messages or provider messages are more effective at decreasing ED visits within the 30 days following a procedure by running an OLS regression with a binary outcome variable coding for ED visits (1 = visit, 0 = no visit) and a dummy-coded predictor variable coding for condition (1 = tele-nurse, 0 = provider).

**Question 3:** Do messages that encourage calls to the tele-nurse decrease ED visits compared to sending no messages?

*Analysis 3 (Confirmatory):* We will test the hypothesis that patients who are sent messages encouraging them to call the tele-nurse line are less likely to visit the ED within the 30 days following their procedure than those who are not sent messages. We will run an OLS regression with a binary outcome variable coding for ED visits (1 = visit, 0 = no visit) and a dummy-coded predictor variable coding for condition (1 = tele-nurse message, 0 = no message).

**Question 4:** Do messages that encourage patients to call their provider increase calls compared to sending no messages?

*Analysis 4 (Confirmatory):* We will test the hypothesis that patients who are sent messages encouraging them to call their provider are less likely to visit the ED within the 30 days following their procedure than those who are not sent messages. We will run an OLS regression with a binary outcome variable coding for ED visits (1 = visit, 0 = no visit) and a dummy-coded predictor variable coding for condition (1 = provider message, 0 = no message).

### **Notes, sensitivity analyses and robustness checks**

*Primary Outcome 1* determines if the patient makes *any* phone call about their procedure to their provider or the tele-nurse line, regardless of their condition. For example, a provider call from a patient in the tele-nurse condition will count as a call, even though the patient did not call the number instructed in the message. This approach allows us to control for the fact that provider phone numbers are better known than the tele-nurse phone number, so there will be a higher rate of provider calls compared with tele-nurse calls, regardless of message condition.

It is difficult to determine if a call is about the patient's procedure. The team is preemptively removing from the dataset reasons that are not relevant to procedures (see list below) as determined by clinical partners. However, it is not possible to anticipate all call reasons that may

be relevant or irrelevant to the precipitating procedure. The team will clean the data again prior to analysis using the following method:

- The study team will aggregate *all* call reasons entered in the EHR for calls from all study participants.
- The team's clinical partners, blind to the patients' experimental conditions, will sort the reasons into those that are likely to be about the procedure and those that are not relevant to the procedure. Alternatively, a non-expert on the study team may pre-sort reasons blind to experimental conditions, and clinical partners will confirm the pre-sorted list.

Analyses of the primary outcome will be limited to calls about the procedure. A robustness check will include data for all calls (except those preemptively filtered from the dataset) from study patients, regardless of the call reason. A more restrictive robustness check will also be conducted, excluding data for calls with more ambiguous reasons that may only occasionally be relevant to the patient's procedure.

*Primary Outcome 2* focuses on ED visits and includes any ED visit regardless of reason, as even seemingly irrelevant visits (e.g., for a car accident) may be in some way related to the patient's procedure. If sufficient data are available to assess ED visit reasons, we may run a robustness check including only reasons deemed relevant to the patient's procedure by our clinical partners.

Recent work suggests that OLS regressions are appropriate in randomized experiments with binary outcome variables such as ours (Gomila, 2021). However, as a robustness check, we will also run the regressions described above as logistic regressions instead of OLS regressions.

As an additional robustness check, we will run OLS regression analyses controlling for sex, binned age (18–24, 25–34, 35–44, 45–54, 65+), and interactions among sex and age as covariates.

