### *Secondary Outcomes*

We will use the approaches described above to evaluate the impact of the intervention on the secondary outcome measures listed in the pre-registration:

1. Phone calls [ Time Frame: 12 months ]
2. ED utilization [ Time Frame: 12 months ]
3. Phone calls – surgical patients only [ Time Frame: N = 17,300 or 18 months, whichever occurs first ]
4. ED utilization – surgical patients only [ Time Frame: N = 17,300 or 18 months, whichever occurs first ]
5. Phone calls – surgical patients only [ Time Frame: 12 months ]
6. ED utilization – surgical patients only [ Time Frame: 12 months ]

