## 3. Patient portal messages

In addition to testing whether calls differ by message condition, we will also examine if patients in either condition are more likely to send a patient portal message to their provider. It is plausible that portal messaging may be affected since the intervention involves contact via the patient portal. We will run all analyses proposed for the first primary outcome (phone calls) on patient portal messages to test this question.

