## 5. Age

Patients of different ages may respond differently to our different message conditions. For instance, patients of some ages might feel more comfortable calling their provider, while patients of other ages might be more inclined to call the tele-nurse. We will test for this possibility by running an OLS regression including binned age (18–24, 25–34, 35–44, 45–54, 65+), experimental group, and their interaction.

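### The age bins leave out ages 55–64 in both the covariate-adjusted check and the age-by-condition analysis, with no rule for these patients

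*SAP*

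**What the plan says.** Under the notes on sensitivity analyses and robustness checks, the SAP repeats the OLS regressions "controlling for sex, binned age (18–24, 25–34, 35–44, 45–54, 65+), and interactions among sex and age as covariates". Under Additional exploratory analyses, item 5 (Age), it tests whether the effect of the messages varies with age by an "OLS regression including binned age (18–24, 25–34, 35–44, 45–54, 65+), experimental group, and their interaction". The two lists are identical.

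Two other sections extend the reach of the first list. For the six secondary outcomes the SAP says: "We will use the approaches described above to evaluate the impact of the intervention on the secondary outcome measures". For portal messages (exploratory item 3) it says: "We will run all analyses proposed for the first primary outcome (phone calls) on patient portal messages".

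The planning population is described as "Women's Health patients who underwent surgical or clinical procedures". No section states an upper age limit, an exclusion of ages 55–64, a reference age category, or a rule for a patient whose age fits no bin.

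**The concern.** A bin list for a regression covariate has to cover every patient in the model. This one stops at 54 and resumes at 65, so the analyst must decide what to do with a decade of age, and the SAP does not decide it.

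Common coding leads to one of two results:

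- **Age category set to missing.** The patient drops out. The adjusted check then covers a narrower population than the analysis it is meant to check, so a difference between the two could come from the lost age group rather than from adjustment. The age-by-condition analysis would say nothing about ages 55–64.
- **Zero on every age dummy.** The patient joins the reference bin. In the adjusted check this only makes the adjustment coarser. In the age-by-condition analysis the reference bin's message effect becomes a blend of two separate age groups, and every interaction term is read against it.

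Neither route biases the arm comparison in the adjusted check, because the arms remain randomised among the patients retained. What is at stake is the coverage and precision of that check, and the meaning of the exploratory age result.

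**Working it through.** **1. Coverage.** Each whole-number age from 18 to 100 was compared with the five bins. The uncovered ages are exactly 55, 56, 57, 58, 59, 60, 61, 62, 63 and 64. With a 55–64 bin added, no age from 18 upward is uncovered.

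**2. The SAP's own power figure.** Inputs from the Power Analysis section are a control ED rate of 5.8%, a 20% relative reduction, two-sided 0.05 and 5,766 per arm. The reduced rate is 0.8 × 5.8% = 4.64%, which the SAP prints as 4.6%. With the unpooled normal approximation:

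- SE = √[(0.058 × 0.942 + 0.0464 × 0.9536) / 5,766] = √(0.09888 / 5,766) = 0.004141
- z = 0.0116 / 0.004141 = 2.801
- Power = Φ(2.801 − 1.960) = Φ(0.841) = 0.800

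This reproduces the stated figure of about 80%. A pooled-variance calculation gives 5,771 per arm, also in agreement. Using the rounded 4.6% instead would give power of 0.827, so the stated sample size rests on the unrounded reduction.

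**3. If patients aged 55–64 are dropped.** Let f be their share. The SAP gives no age distribution, so the values of f below are assumptions. The arm size becomes 5,766 × (1 − f), the SE grows by 1/√(1 − f), and power is Φ(2.801 × √(1 − f) − 1.960). The last column applies the planning contrast to the reduced sample, ignoring any precision gained from the covariates.

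| Assumed f | Dropped of 17,300 | Per arm | SE ratio | Power |
|---|---|---|---|---|
| 0 | 0 | 5,766 | 1.000 | 0.800 |
| 2% | 346 | 5,651 | 1.010 | 0.792 |
| 5% | 865 | 5,478 | 1.026 | 0.779 |
| 10% | 1,730 | 5,189 | 1.054 | 0.757 |
| 15% | 2,595 | 4,901 | 1.085 | 0.733 |

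**4. If they are merged with the reference bin.** Let r be the true reference bin's share of all patients. Patients aged 55–64 then make up w = f / (f + r) of the combined bin.

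| Assumed f | w if r = 10% | w if r = 40% |
|---|---|---|
| 2% | 17% | 5% |
| 5% | 33% | 11% |
| 10% | 50% | 20% |
| 15% | 60% | 27% |

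Both values of r are assumptions, since the SAP names no reference bin. Write d_ref, d_gap and d_k for the message effects in the reference bin, at ages 55–64 and in another bin k. In expectation the combined reference effect is (1 − w) × d_ref + w × d_gap. The interaction for bin k therefore estimates (d_k − d_ref) + w × (d_ref − d_gap). The second term is an unintended shift, common to all the interactions. It vanishes only if ages 55–64 respond exactly as the reference bin does.

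**5. What is not touched.** The confirmatory regressions for phone calls and ED utilization have condition as their only predictor, as do their logistic versions. The sample size was derived without age.

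**The case against.** The strongest reply is that this is a small slip in a minor place. It affects one additional robustness check and one exploratory analysis, and in the robustness check neither coding route biases the arm comparison. The regular ten-year steps from 25 onward suggest a category lost in drafting, which anyone tabulating age would notice and repair. An analyst might simply add the bin or merge these patients with a neighbouring one, and then neither scenario above would arise. The sizes depend on assumed shares: with a 40% reference bin the blend is 5% to 27%, not 17% to 60%. The SAP also claims no power for the adjusted check. Finally, the top bin may have been meant to start at 55.

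Much of this stands. The confirmatory results are safe, the true size is unknown, and the two coding routes are common ones rather than the only ones. It does not remove the point. The same list appears twice, so a text-extraction fault is unlikely. The available repairs give different models, and the SAP selects none of them. In the age-by-condition analysis, age is the question itself. That the cause is probably a slip is a reason to correct it in writing, not to leave it to whoever runs the model.

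**Conclusion.** The concern holds. As written, the bins omit ages 55–64 in two prespecified analyses. On the SAP's wording, the gap in the adjusted check also carries into the secondary outcomes and the portal-message analyses.

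The consequences are limited to those analyses. If the patients are dropped, the adjusted check loses coverage and some precision: about 1.0% to 8.5% on the standard error for assumed shares of 2% to 15%. If they are merged, the age-by-condition analysis is read against a blended reference group whose make-up depends on two shares that the SAP does not give. The gap itself is certain from the text; its numerical effect is not. It should be fixed, but it does not threaten the confirmatory conclusions.

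**What to change.** State the bins in both places (the covariate-adjusted robustness check and exploratory item 5) as 18–24, 25–34, 35–44, 45–54, 55–64 and 65+. This keeps every printed bin and closes the gap exactly. If the team in fact meant the top bin to start at 55, it should say so in writing. Either way, the choice should not depend on the outcome data. Naming the reference bin at the same time would remove the remaining ambiguity in the interaction model.

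Make the change before any analysis that uses age. That includes the 12-month secondary outcomes if they are analysed ahead of the 18-month ones, a timing the SAP does not give.

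The cost is one bin added in two places, with no new data and no change to the confirmatory analyses or the sample size.

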### *Secondary Outcomes*

We will use the approaches described above to evaluate the impact of the intervention on the secondary outcome measures listed in the pre-registration:

1. Phone calls [ Time Frame: 12 months ]
2. ED utilization [ Time Frame: 12 months ]
3. Phone calls – surgical patients only [ Time Frame: N = 17,300 or 18 months, whichever occurs first ]
4. ED utilization – surgical patients only [ Time Frame: N = 17,300 or 18 months, whichever occurs first ]
5. Phone calls – surgical patients only [ Time Frame: 12 months ]
6. ED utilization – surgical patients only [ Time Frame: 12 months ]

### **Additional exploratory analyses**

1. Phone calls to provider vs. tele-nurse

Our primary outcome does not distinguish calls to the provider from calls to the tele-nurse line. This analysis will test the hypothesis that participants in the provider condition call their providers at higher rates than those in the tele-nurse condition, and conversely,

whether those in the tele-nurse condition call the tele-nurse at higher rates than those in the provider condition.

To test this hypothesis, we will run two separate regressions: one for calls to the provider and one for calls to the tele-nurse line. In each regression, we will include a dummy coded variable for patient condition (provider, tele-nurse, control).

## 2. Visit acuity

It is important to prevent unnecessary ED visits without discouraging patients from visiting the ED when necessary. We will therefore assess the relationship between message condition and ED visit acuity. Acuity levels will be derived from the visit acuity level in the patient's electronic health record, and/or will be based the NYU ED Algorithm, depending on data availability.

## 3. Patient portal messages

In addition to testing whether calls differ by message condition, we will also examine if patients in either condition are more likely to send a patient portal message to their provider. It is plausible that portal messaging may be affected since the intervention involves contact via the patient portal. We will run all analyses proposed for the first primary outcome (phone calls) on patient portal messages to test this question.

## 4. Timing of ED visit

Patients who seek care at night or on the weekend may have fewer alternative options compared to patients who seek care during the weekday during normal clinic hours. We will test whether the effect of messages on ED visits is particularly pronounced during the daytime hours by running an OLS regression with a binary timing variable (1 = normal clinic hours, 0 = off hours [night time or weekend]), experimental group, and their interaction.

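### The exploratory ED-timing regression states no outcome coding, row unit or timing value for non-visitors, and with the SAP's only coded ED outcome it cannot test its hypothesis

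*SAP*

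**What the plan says.** The SAP, Additional exploratory analyses, item 4 (Timing of ED visit), sets out its aim: "We will test whether the effect of messages on ED visits is particularly pronounced during the daytime hours". The method is "running an OLS regression with a binary timing variable (1 = normal clinic hours, 0 = off hours", the latter meaning night or weekend, with "experimental group, and their interaction" as the remaining terms. The item gives no coding for the dependent variable. It does not say whether a row is a patient, a visit or a patient-by-period record, and it gives no timing code for a patient who never visits the ED.

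The only ED outcome coded anywhere in the SAP is under Primary Outcomes, item 2: "a binary outcome variable coding for ED visits (1 = visit, 0 = no visit". It is defined per patient over a fixed window, since the hypothesis is that messaged patients are "less likely to visit the ED within the 30 days following their procedure than those who are not sent messages".

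**The concern.** The model has the same form as the age analysis in item 5 of the same section: a covariate, experimental group and their interaction. That form works for age because every patient has an age before randomisation. Visit timing is different. It is a property of the visit, it arises after randomisation, and it is undefined for anyone without a visit.

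An analyst following the text must therefore choose an outcome, a row unit and a rule for non-visitors. The natural choice of outcome is the one the SAP already codes. If the listed terms cannot answer the question with that outcome, the analysis either fails when it is run or returns an interaction that does not mean what item 4 says it tests.

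**Working it through.** **Inputs from the SAP.** Control ED rate: "5.8% ED utilization rate based on historic data" (Power Analysis). Planned effect: a 20% relative reduction, so 0.058 × 0.8 = 0.0464, a fall of 1.16 points. Arms (Estimated Sample Sizes): control 5,766; messages 5,767 + 5,767 = 11,534; total 17,300.

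**Assumptions, not in the SAP.** At most one ED visit per patient; message arms pooled; clinic-hours share of control visits 40%, with 25% and 55% as a range.

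**The plan's own figure.** For 5.8% against 4.64%, two-sided 0.05, the usual two-proportion formula gives 5,771 per group for 80% power, and 79.97% power at 5,766. The stated 5,766 reproduces. The SAP gives no figure for the timing analysis itself.

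**Step 1: who has a timing value.** With the planned reduction in both message arms: 5,766 × 0.058 + 11,534 × 0.0464 = 334.4 + 535.2 ≈ 870, and 870 / 17,300 = 5.0%. With no effect: 17,300 × 0.058 ≈ 1,003, or 5.8%. So 94% to 95% of patients have no timing value.

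**Step 2: any-visit outcome, non-visitors dropped as missing.** Every remaining patient has outcome 1. The fit is intercept = 1, with timing, group and interaction all 0. Nothing can be tested. One row per visit has the same defect.

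**Step 3: any-visit outcome, non-visitors coded timing = 0** (a step the SAP does not state). Write d and o for the clinic-hours and off-hours visit rates, with subscript 0 for control and 1 for message. The model is saturated, so its coefficients are differences of cell means:

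- timing = 1: everyone visited, so the mean is 1 in both groups;
- timing = 0: the mean is o / (1 − d).

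Message coefficient = o1/(1 − d1) − o0/(1 − d0).

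Interaction = (1 − 1) − message coefficient = minus the message coefficient, exactly, for any clinic-hours share.

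At a 40% share, d0 = 0.0232 and o0 = 0.0348, so o0/(1 − d0) = 0.0348/0.9768 = 0.03563.

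- Whole 1.16-point reduction in clinic hours: d1 = 0.0116, o1 = 0.0348; 0.0348/0.9884 = 0.03521; interaction +0.0004.
- Equal 20% relative reduction in both periods: d1 = 0.01856, o1 = 0.02784; 0.02784/0.98144 = 0.02837; interaction +0.0073.

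Across shares of 25% to 55%, the first case gives +0.0005 to +0.0003 and the second +0.0089 to +0.0055. The term stays near zero when the hypothesis is fully true and moves when off-hours visits fall.

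**Step 4: two rows per patient, one per period.** Interaction = (d1 − d0) − (o1 − o0). At a 40% share:

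- whole reduction in clinic hours: −0.0116 − 0 = −0.0116;
- equal 20% relative reduction: −0.00464 + 0.00696 = +0.0023.

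Here the term does measure the difference between the daytime and off-hours effects, on the absolute scale. The SAP does not describe this layout.

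**The case against.** The strongest reply is that item 4 never says its dependent variable is the any-visit outcome. Its three terms are exactly those needed in a patient-by-period layout, so this is an omission rather than a wrong model. That is fair as far as it goes: a reader might infer that the SAP commits to an invalid regression, and the text does not support that, because the outcome is left unstated. What stands is that no section supplies the missing outcome, row unit or rule for non-visitors, and that the one ED outcome the SAP does code fails. It is also fair that either failing layout would probably be noticed when run: all slopes are 0 in one, and the timing coefficient is about 0.96 by construction in the other.

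A reader might also infer a contradiction of scale, because OLS compares absolute reductions while Change in Time Frames says "At 18 months, we expect to be powered to detect a 20% relative decrease in ED utilization". The documents do not support that. OLS on a 0/1 outcome implies the absolute scale once the outcome is fixed, and the relative figure is planning language for a detectable effect, which Power Analysis also gives as two absolute rates. Absolute and relative comparisons can differ when the periods have different base rates, as the +0.0023 under equal relative reductions shows, but this is a reason to report both, not an error in the plan.

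**Conclusion.** The point holds as a minor specification gap with a real consequence: the listed regression, run on the SAP's own ED outcome, cannot show whether the message effect is larger in clinic hours. Both failures are algebraic and do not depend on the assumed clinic-hours share. They also hold with a separate indicator for each message arm. Only the illustrative sizes (+0.0004 against +0.0073 at a 40% share) rest on that share, on one visit per patient and on pooled message arms.

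Nothing here touches the confirmatory analyses. A reader might infer that the ED results or the sample size are in doubt; they are not, because this is one of five additional exploratory analyses and the primary ED models are coded separately.

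**What to change.** In item 4, define two binary outcomes for every randomised patient over the 30 days after the procedure: any clinic-hours ED visit and any off-hours ED visit. Patients without a visit score 0 on both, and a patient with both kinds of visit scores 1 on both. Regress each outcome on condition.

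To compare the two effects, stack two rows per patient and regress the 0/1 outcome on period, condition and their interaction, with standard errors clustered on patient. State that the interaction is a difference in absolute risk differences, and whether condition is pooled or kept as three arms. Reporting the relative reduction in each period alongside it is an optional addition.

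The cost is a few sentences of SAP wording and a few lines of code. It needs no new data and no change to sample size. The SAP says data collection is still under way, so the wording can be settled before analysis.
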